The oval foramen remains pervious after birth in about 20% of the population and predominantly in female subjects. Closure of the oval foramen pervio (PFO) resulted in a partial or complete regression of migraine symptomatology in several retrospective and monocentric^{studies 4-6}. In these studies, percutaneous correction of PFO had been performed for the secondary prevention of stroke⁴ or for the presence of conditions related to intracardiac shunt such as decompression sickness in divers⁶. Since there are no diagnostic or provocative tests capable of correlating PFO to migraine, it is difficult to understand which patients will be responsive to the elimination of the right-left intracardiac shunt after correction of PFO.

Other possible clinical benefits of PFO closure include reducing the sequelities of a paradoxical embolism such as ischemic stroke, myocardial infarction^{11,12} and cognitive impairment.

Although it has not been documented, the prevention of chronic headache through the correction of PFO in the earliest and phase phase of the disease can also be beneficial. Current estimates indicate that 4% of the general population suffers from chronic migraine¹³ which in 75% of cases is the result of a transformation from a phasic or periodic migraine.¹⁴ Eradication of the source of migraine can also be positive against these progressive pathological processes. However, to date, international guidelines (ESC and AHA/ACC) do not include migraine among the indications to the correction of PFO.

he prevalence of PFO in subjects with migraine with aura varies between 41% and 89%⁴, while it is between 7% and 34% in symptomatic patients for migraines without aura and between 20% and 25% in controls without migraine⁴.

This association is two-way because the risk of developing a neurological ischemic event in a subject with PFO and migraine is 5.1 times higher (95% CI, 4.67 -5.59) than in a subject without PFO⁹ and young women are more frequently symptomatic for migraine when affected by PFO.

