The premium (Prospective, Randomized Investigation to Evaluate Incidence of Headache Reduction in Subjects With Migraine and PFO Using the AMPLATZER PFO Occluder to Medical Management) study hypothesis was based on the possible significant reduction in the frequency of migraine attacks with and without aura after percutaneous correction of PFO and broad dx-sin shunt in patients symptomatic for migraine from 6 to 14 days/month and not responsive to drug therapies. The primary endpoint of the study was to reduce the frequency of migraine attacks (with or without aura) by at least 50%; the proportion of patients with headache reduction was superimposable in the PFO correction group (38.5%) and in that addressed to medical therapy (32%), $p=0.32$. With regard to secondary endpoints, there was a significant reduction in the number of migraine days/month after CORRECTION of PFO compared to the control group (-3.4 ± 4.4 days versus -2.0 ± 5.0 days ($p = 0.025$)). No difference was observed in the percentage of patients who achieved a 75% reduction > migraine attacks while a very significant difference was observed with regard to subjects who experienced a complete regression of migraine episodes: 8.5% (10/117) in the PFO correction group vs 1.0% (1/103) in the medical therapy group ($p=0.01$). Among these patient responders, 6 were symptomatic for migraine with aura while the other 4 were migraines with isolated episodes of aura.

It could be speculated that the etiological mechanism of headache in patients not subjected to PFO closure could be the activation of platelets inside the tunnel, the overlap between septum primum and secundum, of the patent foramen ovale. This segment, which may be characterized by a potential flow turbulence between the two septa, could lead to platelet activation, especially in the presence of SIA aneurysm. In a small group of patients with migraine, resistance to aspirin has been documented in 24% of subjects, suggesting platelet hyper-reactivity.

Clopidogrel and aspirin are more effective than aspirin alone in reducing headache, exacerbated after percutaneous correction of PFO in the first follow-up period²⁴ to demonstrate that platelet microaggregates may be responsible for post-closure migraine of PFO and may play a central role in the genesis of headache.

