In women and patients with stable coronary artery disease, in antiplatelet therapy with aspirin, high platelet reactivity (HAPR) or resistance to aspirin has been described and is associated with adverse clinical outcomes. A study conducted by Jesurum et al, suggested that subjects with migraine have a higher prevalence of HAPR than healthy subjects or patients with stable coronary artery disease being treated with aspirin 325 mg. However, the clinical implications of HAPR in subjects with migraine and PFO require further investigation of analysis for the high risk of cerebral stroke and myocardial infarction and the need to prescribe early prevention therapy.

A PFO with dx-sin shunt should require a neurological substrate susceptible and vulnerable to some substance that by-passes the pulmonary circle and induces headache. The endothelium of the

Protocol number

NCT03521193

pulmonary circle has significant metabolic activity. The lung in fact metabolizes, activates or inactivates many compounds including vasoactive amines and other humoral substances²⁵. Prostaglandins E1, E2 and F2 are completely removed from the bloodstream; serotonin is removed between 85% and 95%; 70% of angiotensin I is converted to angiotensin II, and 80% of bradykinin is inactivated²⁶. It is not known whether these substances may increase the susceptibility of the brain to stimulate environmental or intrinsic triggers capable of triggering migraine

Objectives and aims of the study

The aim of the study is to verify whether vasoactive/inflammatory substances together with increased platelet reactivity may play a key role in the onset of migraine and in its maintenance even after correction of PFO. The morphological and anatomical characteristics of the oval fossa will also be analyzed in order to identify elements that can correlate with increased platelet reactivity and predict a clear benefit in the control of migraine symptoms after correction of PFO. The analysis will also be extended to the evaluation of differences between female and male sex.

4. Study design

1. 4.1 Primary and secondary outcomes

Primary outcomes:

Evaluation of the % regression of migraine episodes with aura in relation to platelet reactivity in migraine patients, with and without aura, carriers of PFO, together with the dosage of PGE1, PGE2, serotonin and cytokines in order to identify potential predictive markers of beneficial effect of PFO correction on migraine symptoms.

Secondary outcomes

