1. Reduction in the number of migraine days compared to pfo pre-correction, FU at 6 and 12 months.

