4.2 Study design

The study is prospective observational, monocentric

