5.0 Characteristics of the population

The study population includes patients with patent foramen ovale and previous neurological event (TIA or stroke) with clinical indication to the percutaneous correction of the defect according to guidelines or in a previous TIA/stroke absence when addressed to the pfo treatment for migraine non responsive to specific therapy, as per the evaluation of the neurologist specialist. Similar evaluations are not currently available in the literature able to identify patients who, not responsive to specific drug therapy, as prescribed by the neurologist specialist, and carriers of PFO, can be directed to the percutaneous correction of the defect with indication at the moment "off-label" with respect to what is codified by the international guidelines (ESC and AHA / ACC) but potentially effective in the control of symptomatology. The advantage of PFO correction observed so far only in patients undergoing PFO correction as a result of cerebral ischemic events, could translate into migraine workers in a reduction in costs borne by the National Health System in the number of neurological medical examinations, pharmacological prescriptions and missed working days.

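### Section 4.1 seeks markers that predict the benefit of PFO closure, but every followed patient is closed, so the plan can show only which markers go with migraine change after closure

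*Combined protocol and SAP*

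**What the plan says.** The primary outcome in section 4.1 relates regression of migraine to platelet reactivity and to PGE1, PGE2, serotonin and cytokine levels, "in order to identify potential predictive markers of beneficial effect of PFO correction on migraine symptoms". Phase 2 in section 6.1 likewise takes a beneficial effect of closure as the thing to be explained.

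The purpose is stated in two places. The background says that "it is difficult to understand which patients will be responsive to the elimination of the right-left intracardiac shunt after correction of PFO". Section 5.0 wants to identify drug-refractory migraine patients who, as "carriers of PFO, can be directed to the percutaneous correction of the defect", would receive it outside current guidelines.

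On design, section 4.2 says only: "The study is prospective observational, monocentric". Section 5.0 admits patients with a guideline indication for closure after TIA or stroke, or, "in a previous TIA/stroke absence when addressed to the pfo treatment for migraine non responsive to specific therapy". The secondary outcome in 4.1 is "Reduction in the number of migraine days compared to pfo pre-correction". Section 9.1 compares responders with non-responders. Section 9.2 sizes the study on the correlation between change in the Anzola score and any of five baseline factors.

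**The concern.** A marker predicts the effect of closure if the difference between what happens with closure and what would have happened without it varies with the marker. A marker is prognostic if it is related to how patients fare whatever is done. Separating the two needs information on patients who are not closed, and this study has none. Natural course, regression to the mean, placebo response and ongoing care all enter the measured change. Antiplatelet treatment around the procedure may also contribute, though how much is uncertain because aspirin is already in place beforehand.

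A prognostic marker can therefore pass the planned tests and be reported as a marker of closure benefit. The stated use is choosing patients for an implant procedure outside guidelines, and a marker of who improves anyway would be no guide to that choice.

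**Working it through.** **1. Who supplies the data.** Set side by side, the planned comparisons are:

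- section 4.1, secondary outcome: each patient against their own pre-closure value;
- section 6.1: migraine score before closure and at 6 and 12 months after it; platelet function before closure and 180 days after it;
- section 9.1: responders against non-responders;
- section 9.2: score change against baseline factors.

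All are within closed patients. No marker-by-closure comparison is planned, and the randomisation heading (4.8) is unfilled.

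**2. The plan's own sample size.** Inputs from 9.2: r = 0.35, alpha 0.01 (0.05/5), power 80%, 4 covariates. Two-sided testing is assumed. Fisher's z gives n = ((2.576 + 0.842)/atanh(0.35))² + 3 + k, with atanh(0.35) = 0.3654.

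- k = 0: 87.45 + 3 = 90.45, so 91.
- k = 4: 94.45, so 95.

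Power at 92 is Φ(√(89 - k) × 0.3654 - 2.576) = 0.808 for k = 0 and 0.786 for k = 4. The planned 92 is therefore a one-group calculation for association.

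**3. The section 9.2 test applied to a purely prognostic marker.** Suppose the marker correlates 0.35 with migraine change equally with and without closure, so that it says nothing about closure benefit. The test sees only the closed patients, so its power is the same 79-81%. A simulation (20,000 runs, no covariates) flagged the marker in 81% of 92-patient closure-only studies. A comparison of correlations between 92 closed and 92 non-closed patients flagged it in 1.0%, the nominal rate. This follows from the design and does not depend on any outside data.

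**4. How much improvement might occur without closure.** The Rational section reports one randomised trial. Medical-therapy result as a share of the closure result:

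| Measure | Medical therapy / closure | Share | 95% CI |
|---|---|---|---|
| At least 50% reduction | 32% / 38.5% | 83% | 58% to 120% |
| Migraine days per month | -2.0 / -3.4 | 59% | 30% to 95% |
| Complete regression | 1.0% / 8.5% | 12% | 1.5% to 87% |

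The complete-regression counts are given: "8.5% (10/117) in the PFO correction group vs 1.0% (1/103) in the medical therapy group". The other intervals assume the same denominators. On that assumption the responders are 45/117 and 33/103, a difference of 6.4 points (95% CI -6.2 to +19.0). The chi-square p is 0.320, matching the reported 0.32. The days interval uses Fieller's method with the reported SDs of 4.4 and 5.0.

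**5. The responder test of section 9.1.** Assumptions: 92 patients; three groups (responds anyway, responds only because of closure, does not respond); closure harms no one; a normal marker with SD 1 shifted by d in one kind of responder only; pooled t-test; 40,000 runs. The table gives the chance of two-sided significance at 0.01 for d = 0.8, with 0.05 (the level in 9.3) in brackets.

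| Response without / with closure | Marker of background response only | Marker of closure benefit only |
|---|---|---|
| 32% / 60% | 24% (47%) | 17% (37%) |
| 32% / 38.5% | 66% (85%) | 2.6% (10%) |
| 1.0% / 8.5% | 1.5% (6%) | 24% (45%) |

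The 60% is the frequency assumed in 9.2; the other rates are from the cited trial. Over d = 0.5 to 1.0 at the 0.01 level, the ranges are 8-39% v 6-27%, 25-86% v 1.6-3.6%, and 1.3-1.8% v 8-39%. With d = 0 the rate is 1.0-1.1%.

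**6. What a comparator would take.** Testing 0.35 with closure against an assumed 0 without it (two-sided 0.01, 80% power, 1:1, 4 covariates) needs n per group = 2 × 87.45 + 3 + 4 = 181.9, so 182, or 364 in all. For 0.35 against 0.10 the total is 680. The documents give no correlation without closure.

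**The case against.** The strongest objection is that the size of the problem depends on the endpoint. If response means complete regression, the cited trial suggests that few patients would respond without closure, so nearly all responders would owe it to closure. The primary outcome speaks of regression of episodes with aura, and the trial summary gives no medical-therapy rate for that. The 83% may therefore not be the relevant figure. This stands as a limit on magnitude. It does not rescue the aim: no responder cut-off is given, section 7.1 is blank, 9.2 sizes a score change, and the benign case works only by borrowing a control rate from another population with an active comparator, with an interval of 1.5% to 87% on the ratio.

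It can also be said that the plan calls its markers potential, uses the language of correlation, and adjusts for four confounders. The word potential softens certainty but leaves the target unchanged; repeating the same association in a larger closure-only cohort would be equally ambiguous. The four covariates are unnamed, and adjustment does not supply a comparator.

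Finally, no passage sets a rule for choosing closure by marker, and the simulation rests on assumed shifts and a simple three-group model that mixes sources in its first scenario. Both are fair. The harm lies in what the plan allows to be concluded, and the simulation illustrates an argument that does not need it.

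**Conclusion.** The concern holds. The aim in 4.1 is a claim about variation in the effect of closure, and a study in which every followed patient is closed cannot support it. It can support a statement about which baseline markers are associated with migraine change after closure.

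The logical point needs only the absence of a non-closure group. Its practical size depends on how much improvement would occur without closure, which the documents do not give for this population. On the cited trial's figures it would be large for a 50% cut-off and nearly absent for complete regression. The oval-fossa aim in the objectives section was not part of this point.

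**What to change.** 1. In section 4.1, restate the objective as: baseline markers associated with change in migraine after PFO closure. State there that this single-arm study cannot separate markers of closure benefit from markers of background improvement or of response to co-treatment, and that a positive marker is therefore not to be reported as a criterion for selecting patients for closure (the use foreseen in 5.0).
2. In Phase 2 of section 6.1, keep the planned platelet comparison and add one sentence: a platelet change, or a correlation with response, does not by itself show that the improvement was caused by closure.

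The cost is wording only. No data, visits or analyses are added, and the 92 patients are unchanged. The one downside is a more modest claim. A concurrent non-closure group would be needed to keep the present aim, but on the assumptions shown it would take several hundred patients, so it is not proposed here.

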8.4 Type and duration of subjects following adverse events

9. statistical analysis

9.1 statistical analysis

Continuous variables will be summarized using the DS \pm mean. Categorical variables are represented using frequencies and percentages. For the comparison between responders and non-responders, the Student's 2-code t-test or the Wilcoxon test for continuous variables will be used. The Chi-square test or the Fisher test will be used for categorical variables.

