9.2 Calculation of the sample number

The sample size calculation is based on the 1-year primary endpoint. A value for the frequency of reaching the primary endpoint was placed around 60%, in accordance with the data reported in

Protocol number

NCT03521193

literature^{22, 27}. A sample of 92 patients was identified, necessary to obtain a potency of 80% able to detect as significant ($p < 0.01$, considering the Bonferroni correction for multiple tests) a correlation coefficient of 0.35 (adjusted for 4 confounding variables) between the variation of the migraine score sec. Anzola and any of the 5 factors (platelet reactivity, PGE1, PGE2, cytokines, serotonin) measured at baseline.

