9.3 Significance level to use

Statistical significance will be considered that obtained with a p value of 0.05.

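### The plan aims to find markers that predict benefit from PFO closure but specifies only tests of association, so a significant result would not show how well a marker identifies responders

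*Combined protocol and SAP*

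**What the plan says.** The primary outcome in section 4.1 relates regression of migraine episodes to platelet reactivity and to the measured substances, "in order to identify potential predictive markers of beneficial effect of PFO correction on migraine symptoms". Section 5.0 gives the background: the literature offers no similar evaluation able to identify which drug-refractory patients with a PFO "can be directed to the percutaneous correction of the defect", an indication it calls off-label. Section 6.1 sets out to characterise patients as responders or non-responders.

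The statistical text is short:

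- **Section 9.1** gives descriptive summaries and then tests of difference. "For the comparison between responders and non-responders", "the Student's 2-code t-test or the Wilcoxon test for continuous variables will be used", with chi-square or Fisher tests for categorical variables.
- **Section 9.2** derives 92 patients as "necessary to obtain a potency of 80"% to "detect as significant ($p < 0.01$, considering the Bonferroni correction for multiple tests") "a correlation coefficient of 0.35 (adjusted for 4 confounding variables") between change in the Anzola score and any of five baseline factors. It also places the frequency of reaching the primary endpoint at about 60%.
- **Section 9.3** states a different threshold: "Statistical significance will be considered that obtained with a p value of 0.05".

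The text names no AUC, sensitivity or specificity, cut-off, explained-variance measure or internal validation. *Responder* has no numerical definition, and the endpoint headings in section 7.1 carry no text.

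**The concern.** A test of mean difference or of correlation asks whether marker and outcome are related at all. A predictive marker raises a different question: how far knowing the marker improves the forecast for an individual patient. A correlation can be clearly non-zero and still sort patients poorly.

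The plan answers only the first question, although its aim is worded in terms of the second. With no performance measure planned, significance is the only evidence the analysis would yield for a factor. The factors would also be picked out and described in the same 92 patients, so the apparent strength of those that pass is biased upwards. At stake is how the result may be described. A reader told that a factor predicts benefit would expect evidence on discrimination that the planned analyses do not produce.

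**Working it through.** **Inputs.** From section 9.2: N = 92, r = 0.35, four adjustment variables, five factors, p < 0.01 (0.05/5), power 80%, endpoint frequency about 60%. From section 9.3: p = 0.05. As a lower responder share, 38.5%, the proportion with at least a 50% reduction in the closure arm of the randomised trial described in the Rational section. The correlation test is assumed two-sided; the documents do not say so.

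**1. The plan's own figure.** Partial F-test with one tested and four other predictors:

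- f² = r²/(1 − r²) = 0.1225/0.8775 = 0.1396.
- Denominator df = N − 6; noncentrality λ = f²(N − 4).
- N = 92: df = 86, λ = 0.1396 × 88 = 12.28, power 80.5%. N = 91: power 79.98%.

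So 92 is reproduced. Fisher's z without covariates, ((2.576 + 0.842)/atanh 0.35)² + 3 = 90.5, gives 91; adding four for the covariates gives 95. Two-sided 0.05 would need only 62 to 66. The figure of 92 therefore belongs to two-sided 0.01, and the sample size is not in dispute.

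**2. Smallest correlation that reaches significance.** With 86 df, r = t/√(t² + 86):

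- p < 0.01: t = 2.634, r = 0.273, r² = 7.5%. Without covariates (90 df), r = 0.267.
- p < 0.05: t = 1.988, r = 0.210, r² = 4.4%.

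**3. What these correlations mean for classification.** Let marker X and outcome Y be bivariate normal with correlation r, and let responders be the top share p of Y, with c = Φ⁻¹(1 − p). Then P(responder | X = x) = Φ((rx − c)/√(1 − r²)). Integrating over x gives the marker distributions in responders and non-responders, and from these the AUC, accuracy and response rates.

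| r | Responders | AUC | Best accuracy | Accuracy if all are put in the larger class | Response above / below marker median |
|---|---|---|---|---|---|
| 0.35 (design) | 60% | 0.66 | 64% | 60% | 71% / 49% |
| 0.35 | 38.5% | 0.66 | 65% | 61.5% | 49% / 28% |
| 0.273 (p < 0.01) | 60% | 0.62 | 62% | 60% | 69% / 51% |
| 0.210 (p < 0.05) | 60% | 0.60 | 61% | 60% | 67% / 53% |
| 0.50 | 60% | 0.73 | 68% | 60% | 76% / 44% |
| 0.70 | 60% | 0.83 | 76% | 60% | 84% / 36% |

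The AUC at r = 0.273 is 0.625 before rounding. At r = 0.35 and 60% responders, sensitivity at 90% specificity is 25%, and r² = 12.25%.

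**4. Precision.** With 55 responders and 37 non-responders (60% of 92), the standard error of an AUC of 0.66 is about 0.057, so the 95% CI runs from about 0.55 to 0.77.

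**5. Selection in the same data.** By simulation, if the true r is 0.20, factors that happen to pass p < 0.01 show an average observed r of about 0.33.

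**6. Threshold.** For five independent tests, the family-wise error is 1 − 0.99⁵ = 4.9% at 0.01 and 1 − 0.95⁵ = 22.6% at 0.05.

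**The case against.** The strongest defence is that this is an exploratory, single-centre observational study. Section 4.1 says *potential* markers, and section 6.1 asks whether response may correlate with platelet measures. Correlation is a recognised way to find candidates, and discrimination can be studied later. This stands as far as it goes. It limits what can be demanded of the study, but not the point that performance should be reported, with its uncertainty, if prediction is discussed at all.

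A reader might infer four stronger things that the documents do not support:

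- **That a marker is declared predictive once p < 0.01.** No such rule is written. The 0.01 appears only in the sample-size paragraph, and section 9.3 says 0.05.
- **That a marker at r = 0.35 is barely better than chance.** This is close to fair for accuracy against a 60% base rate, which is an insensitive measure when most patients respond. It is not fair for discrimination: an AUC of 0.66 and a 71% versus 49% split are weak but real.
- **That calling a marker predictive would be wrong.** The 0.35 is a detectable effect chosen for power, not a forecast. A true r of 0.5 or 0.7 would also pass and would perform better. Significance alone simply cannot tell these cases apart.
- **That these results will be used to select patients for closure.** The clause in section 5.0 describes a gap in the literature; it is rationale, not a decision rule.

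**Conclusion.** The point holds in a limited form. The aim is worded as prediction, the planned analyses address association, and significance would support only *associated with change in migraine score*. At the design correlation, discrimination would be weak: AUC about 0.66, with at most 4 percentage points of accuracy gained over calling everyone a responder. A factor can be significant with an AUC of 0.62 to 0.63 at 0.01, or about 0.60 if 0.05 is applied.

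The figures rest on bivariate normality, on the covariate-adjusted correlation standing in for the marker's own, and on responders being the top 60% on Anzola change (the AUC is the same at 38.5%). The Anzola score is a short ordinal sum, so they are approximate. The conclusion that significance does not measure predictive performance needs none of these assumptions.

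**What to change.** In section 9.1:

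1. State the responder definition numerically before analysis.
2. For each of the five factors, report the bootstrap optimism-corrected AUC for responder status at 12 months, with and without the factor added to the covariate model, or the corresponding R-squared gain for Anzola score change, with a 95% CI.
3. Describe factors that pass the significance threshold as *associated with change*, and reconcile the 0.01 of section 9.2 with the 0.05 of section 9.3 so that the threshold is known.
4. Base any statement about predictive value on the size of the corrected AUC or R-squared gain and its CI, not on the p-value or on a CI that merely excludes zero. The latter is only another test against zero. In a simulation of 300 trials with N = 92, four covariates and r = 0.35, such a rule was met in about 71% or 47% of trials, depending on the type of interval.

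All data needed are already being collected, with no extra patients or visits. The cost is analysis code, a few lines of plan text and a more modest claim.
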